## Cohorts 3-4 Dose-Escalation

Conorts 5-4 Dose-Escalation	Screen					Cycle 21 da							Cycle 2 21 day:			Сус (21 с		Addition Cyclo (21 da	es	End of Study or Early Termination
Study Day	-7 to -1	1+	2	4	7*	8	12	15	17	21	22	29	36	37	42	43	63	Every 2	1 days	30 after last Dose
Name of Cycle Day		C1 D1	C1 D2	C1 D4	C1 D7	C1 D8	C1 D12	C1 D15	C1 D17	C1 D21	C2 D1	C2 D8	C2 D15	C2 D16	C2 D21	C3 D1	C3 D21	CX D20	CX D21	51
+/- days allowable				1	1	1	1	1	2	+2	1	1	1	2	1	3	3	4	4	7
Study Drug§		I	NDU	CTIOI	V								М	AINTE	NANC	E				
Study Drugg		Х	Х	Х	Х	Х		Х			Х	Х	Х			Х				
Disease Assessment																				
Bone marrow aspirate and/or biopsy¥	х									х							Х	Every 2-3 cycle		x
Overall Response Rate ‡										Х							Х		Χ‡	Х
Study Procedures & Examinations																				
Eligibility Assessment & Informed Consent	Х																			
Demographics A	Х																			
Medical history B	Х																			
MUGA/ECHO	Х																			
Dilated eye exam with fundus photos N		Х																		
Neurology review and exam 		Х																		
12-lead ECG (QTcF)	Х	X 			X 			X 		Х										
Phys. Exam (inc. weight)	Х	Х			Х			Х		Х	Х				Х	Х	Х		Х	Х
ECOG	Х	Х									Х					Х			Х	Х
Vital Signs (Temp., HR, BP, RR)	Х	X 	X 	X 	X 	X 	Х	X 		Χ	X 	X 	X 	Х	Х	X 	Х		Х	X
Concomitant Medication C	Х	Х	Χ	Х	Х	Х	Χ	Х	Х	Χ	Х	Х	Χ	Х	Х	Х	Х		Χ	X
Adverse Events D		Х	Х	Х	Х	Х	Х	Х	Х	Х	Х	Х	Х	Х	X	Х	Х		Х	X
Labs																				
Pregnancy test	X																			
Blood Hematology E, I, J	Х	X 			X 	X 	Х	X 	Х	Х	Х			Х	Х	Х	Х		Х	X
Chemistry F, I	Х	X 			X 	X 	Х	X 	Х	Х	Х	X 	X 	Х	Х	Х	Х		Х	X
Coagulation, lipase, amylase & urinalysis G, I	Х	X 			X 	X 	Х	X 	Х	Х	Х	X 	X 	Х	Х				Х	Х
Lactate and blood pH I, K	Х	X 	X 	X 	X 	X 	Х	X 	Х	Х	X 	X 	X 	Х	Х	X 	Х		Х	Х
Research Labs																				

Blood collection- pharmacodynamics H	X	X 			X 			X 		Χ									$X^L$
Research Bone marrow aspirate/or biopsy	Х									Χ									
Pharmacokinetics Blood samples I,K,M		X 	X 	X 	X 	X 	Х	X 	Х	Х	X 	X 	X 	Х	Х	X 	Х	Х	X L

Notes and abbreviations provided on following page.

<sup>A including Date of Birth; sex; height; race; ethnicity

<sup>B including oncology history, radiation history

<sup>c name, indication, dose, route, start and end dates

<sup>D starting or worsening after study drug administration (signs and symptoms occurring prior to the first dose of study medication on Day 1 should be recorded under the subject's Medical History).

<sup>E complete blood count, differential, platelets

<sup>F glucose, total protein, albumin, electrolytes [sodium, potassium, chloride, total CO₂], calcium, phosphorus, magnesium, uric acid, bilirubin (total, direct), SGPT (ALT) or SGOT (AST), alkaline phosphatase, creatinine, blood urea nitrogen, CPK

<sup>G PT, PTT, fibrinogen, INR

<sup>HOxygen consumption, metabolites, protein, mRNA analysis

<sup>1 To be performed weekly during the first cycle of the increased dose for any intra-subject dose escalation

<sup>1 For purposes of data collection, test results below the limit of quantitation will be reported as "0"

<sup>K If the Investigator determines that the dose of study drug should be interrupted, additional PK, lactate and blood pH assessments will be collected pre-dose (within 2 hours of dosing) and 4 hours +/- 30 minutes post study drug administration upon resumption of dosing; additional PK assessments may be performed during the interruption at the description of the Investigator. If the dose of study drug is reduced, additional PK assessments will be collected pre-dose (within 2 hours of dosing) prior to starting the reduced study drug dose. Additional unscheduled PK, lactate and pH blood draws may be collected per PI judgement when indicated for further safety follow-up.

<sup>LAdditional PK and/or PD draws from peripheral blood may be obtained ~every 4 days, when possible, for up to 4 weeks after last study drug administration in subjects who discontinue the study.

<sup>M In addition to the time points indicated in the Table, additional draws from peripheral blood for PK analysis may be obtained at the discretion of the Investigator.

<sup>N Baseline dilated eye exam with fundus photos, including distance acuity (visual acuity charts using refraction-based visual acuity measurement), ophthalmoscopy and slit lamp exam, may be performed up to 14 days prior to study drug administration.

<sup>o Baseline neurology review and exam to be performed by consultant neurologist up to 14 days prior to study drug administration. The baseline neurology exam may include, but is not limited to, gait and station, cerebellar functions (coordination), upper and lower extremity reflexes, upper and lower muscle strength and sensation.

<sup>1 collected pre-dose (same calendar day of dosing) and 4 hours +/- 30 minutes post study drug administration

<sup>2 collected pre-dose (same calendar day of dosing) and 2, 4, 6, 8 hours (+/- 30 mins) post study drug administration. Note: vitals may be collected (+/- 60 mins) post study drug administration.

<sup>3 collected pre-dose (same calendar day of dosing)

- \* Treatment will be administered as an inpatient for 24 hours on Day 7 of Cycle 1.
- + Subjects enrolled in the Food Effect group will consume a high fat meal within 30 minutes prior to study drug administration on Day 1 blood sample collection. § Study drug will be administered without food, at least 1 hour before and at least 2 hours after eating, with the exception of Day 1 of Cycle 1 for subjects enrolled in the Food Effect group. Induction or maintenance doses and alternative duration of induction doses or other maintenance schedules of IACS-010759, not to exceed 6 mg, may be pursued depending on the safety and PK/PD data observed.
- ¥ Bone marrow aspirate/biopsy will be performed as clinically indicated, at least once every 3 cycles.
- ‡ Overall Response Rate (ORR) assessment will be performed on the same schedule as bone marrow aspirate/biopsy (every 2-3 cycles during additional cycles). ORR definitions are provided in Section 5.2.2.

Page 34 of 59

Cohorts 5-6 Dose-Escalation and Cohort 7 Dose-Expansion

	Screen					Cycle 21 da							Cycle 2 21 day:			Cyc (21 d		Additio Cycle (21 da	es	End of Study or Early Termination
Study Day	-7 to -1	1+	2	4	5*	8	12	15	17	21	22	29	36	37	42	43	63	Every 2	L days	30 after last Dose
Name of Cycle Day		C1 D1	C1 D2	C1 D4	C1 D5	C1 D8	C1 D12	C1 D15	C1 D17	C1 D21	C2 D1	C2 D8	C2 D15	C2 D16	C2 D21	C3 D1	C3 D21	CX D20	CX D21	51
+/- days allowable				1			1	1	2	+2	1	1	1	2	1	3	3	4	4	7
Study Drug§		II	NDUC	CTION	J P							MA	INTEN	ANCE P						
Disease Assessment																				
Bone marrow aspirate and/or biopsy¥	Х									Х							х	Every 2-3 cycle		Х
Overall Response Rate ‡										Х							Х		X ‡	Х
Study Procedures & Examinations																				
Eligibility Assessment & Informed Consent	Х																			
Demographics A	Х																			
Medical history B	Х																			
MUGA/ECHO	Х																			
Dilated eye exam with fundus photos N		Х																		
Neurology review and exam o		Х																		
12-lead ECG (QTcF)	Х	X 			X 			X 		Х										
Phys. Exam (inc. weight)	Х	Х			Х			Х		Х	Х				Х	Х	Х		Х	Х
ECOG	Х	Х									Х					Х			Х	Х
Vital Signs (Temp., HR, BP, RR)	Х	X 	X 	X 	X 	X 	Х	X 		Х	X 	X 	X 	Х	Х	X 	Х		Х	Х
Concomitant Medication C	Х	Х	Х	Х	Х	Х	Х	Х	Х	Х	Х	Х	Х	Х	Х	Х	Х		Х	Х
Adverse Events D		Х	Х	Х	Х	Х	Х	Х	Х	Х	Х	Х	Х	Х	Х	Х	Х		Х	Х
Labs																				
Pregnancy test	Х																			
Blood Hematology E, I, J	Х	X 			X 	X 	Х	X 	Χ	Х	Х			Х	Х	Х	Х		Х	Х
Chemistry F, I	Х	X 			X 	X 	Х	X 	Χ	Х	Х	X 	X 	Х	Х	Х	Х		Х	Х
Coagulation, lipase, amylase & urinalysis G, I	Х	X 			X 	X 	Х	X 	Х	Х	Х	X 	X 	Х	Х				Х	Х
Lactate and blood pH I, K	Х	X 	X 	X 	X 	X 	Х	X 	Χ	Х	X 	X 	X 	Х	Х	X 	Х		Х	Х
Research Labs																				
Blood collection- pharmacodynamics H	Х	X 			X 			X 		Х										Χ L

Research Bone marrow aspirate/or biopsy	X									Х									
Pharmacokinetics Blood samples I,K,M		X 	X 	X 	X 	X 	Χ	X 	Χ	Χ	$X_3$	X 	X 	Χ	Χ	X 	Χ	Х	$X^{L}$

Notes and Abbreviations:

<sup>A including Date of Birth; sex; height; race; ethnicity

<sup>B including oncology history, radiation history

<sup>c name, indication, dose, route, start and end dates

<sup>D starting or worsening after study drug administration (signs and symptoms occurring prior to the first dose of study medication on Day 1 should be recorded under the subject's Medical History).

<sup>E complete blood count, differential, platelets

<sup>F glucose, total protein, albumin, electrolytes [sodium, potassium, chloride, total CO₂], calcium, phosphorus, magnesium, uric acid, bilirubin (total, direct), SGPT (ALT) or SGOT (AST), alkaline phosphatase, creatinine, blood urea nitrogen, CPK

<sup>G PT, PTT, fibrinogen, INR

<sup>HOxygen consumption, metabolites, protein, mRNA analysis

<sup>1 To be performed weekly during the first cycle of the increased dose for any intra-subject dose escalation

<sup>1 For purposes of data collection, test results below the limit of quantitation will be reported as "0"

<sup>K If the Investigator determines that the dose of study drug should be interrupted, additional PK, lactate and blood pH assessments will be collected pre-dose (within 2 hours of dosing) and 4 hours +/- 30 minutes post study drug administration upon resumption of dosing; additional PK assessments may be performed during the interruption at the description of the Investigator. If the dose of study drug is reduced, additional PK assessments will be collected pre-dose (within 2 hours of dosing) prior to starting the reduced study drug dose. Additional unscheduled PK, lactate and pH blood draws may be collected per PI judgement when indicated for further safety follow-up.

<sup>L Additional PK and/or PD draws from peripheral blood may be obtained ~every 4 days, when possible, for up to 4 weeks after last study drug administration in subjects who discontinue the study.

<sup>M In addition to the time points indicated in the Table, additional draws from peripheral blood for PK analysis may be obtained at the discretion of the Investigator.

<sup>N Baseline dilated eye exam with fundus photos, including distance acuity (visual acuity charts using refraction-based visual acuity measurement), ophthalmoscopy and slit lamp exam, may be performed up to 14 days prior to study drug administration.

<sup>o Baseline neurology review and exam to be performed by consultant neurologist up to 14 days prior to study drug administration. The baseline neurology exam may include, but is not limited to, gait and station, cerebellar functions (coordination), upper and lower extremity reflexes, upper and lower muscle strength and sensation.

<sup>P The dose regimen for the induction and maintenance doses are provided in Table 2.

<sup>1 collected pre-dose (same calendar day of dosing) and 4 hours +/- 30 minutes post study drug administration

<sup>2 collected pre-dose (same calendar day of dosing) and 2, 4, 6, 8 hours (+/- 30 mins) post study drug administration. Note: vitals may be collected (+/- 60 mins) post study drug administration.

<sup>3 collected pre-dose (same calendar day of dosing)

<sup>4 collected pre-dose (same calendar day of dosing) and 2, 4, 6, 8 hours (+/- 30 mins) and 24 hours (+/- 2 hours) post study drug administration. Note: vitals may be collected (+/- 60 mins) post study drug administration.

- \* Treatment will be administered as an inpatient for 24 hours on Day 5 of Cycle 1.
- + Subjects enrolled in the Food Effect group will consume a high fat meal within 30 minutes prior to study drug administration on Day 1 blood sample collection. § Study drug will be administered without food, at least 1 hour before and at least 2 hours after eating, with the exception of Day 1 of Cycle 1 for subjects enrolled in the Food Effect group. Induction or maintenance doses and alternative duration of induction doses or other maintenance schedules of IACS-010759, not to exceed 6 mg, may be pursued depending on the safety and PK/PD data observed.
- ¥ Bone marrow aspirate/biopsy will be performed as clinically indicated, at least once every 3 cycles.
- ‡ Overall Response Rate (ORR) assessment will be performed on the same schedule as bone marrow aspirate/biopsy (every 2-3 cycles during additional cycles). ORR definitions are provided in Section 5.2.2.

IACS2015-001: Protocol Amendment #11 (01-21-20) Page 37 of 59

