#### 4.1.6 Treatment Cohorts and Treatment Schema

In cohorts 1 and 2, IACS-010759 was administered orally daily on a continual 21-day schedule (1 cycle = 21 days of daily dosing), with the exception that the first cycle for each subject contains a 7-day single dose lead-in (first cycle = 28 days). Starting on day 8 of cycle 1 for subjects enrolled in cohorts 1 and 2, dosing is on a 21 day schedule until confirmed PD, initiation of alternative cancer therapy, unacceptable toxicity, or other reasons to discontinue treatment prematurely occur as defined in Section 4.1.9.

Based on PK modeling of data from cohorts 1 and 2, the dose regimen for cohort 3 and subsequent cohorts will change to include an induction phase with daily dosing, followed by a maintenance phase at a dose sufficient to maintain the steady state levels achieved during the induction phase. In these cohorts, IACS-010759 will be administered orally daily (up to 7 days) during the induction phase(Cycle 1, Days 1-7). Starting on day 8 of cycle 1 for all cohorts, maintenance dosing will be administered on a 21-day schedule until confirmed PD, initiation of alternative cancer therapy, unacceptable toxicity, or other reasons to discontinue treatment prematurely occur as defined in Section 4.1.9.

The planned dose levels are given in Table 1 and 2, below:

Table 1: Dosing schema for Cohorts 1 and 2

PHASE	COHORT	NO OF SUBJECTS	IACS-010759 DOSE LEVEL *
Dose-	Cohort 1	3-6	0.5 mg
escalation	Cohort 2	3-6	1 mg

\*Intermediate doses of IACS-010759, not to exceed 8 mg, not listed above may also be pursued with SMC approval, depending on the safety, PK and PD data observed.

Table 2: Revised dosing schema for Cohorts 3-6 (Dose-Escalation) and Cohort 7 (Dose Expansion)

PHASE	COHORT	NO OF SUBJECTS	INDUCTION DOSE* (FREQUENCY#)	MAINTENANCE DOSE* (FREQUENCY#)
	Cohort 3	3-6	2 mg (daily, Cycle 1 Day 1-7)	0.5 mg (once per week)
Dose-	Cohort 4**	3-6	2.5 mg (daily, Cycle 1 Day 1-7)	1.0 mg (three times per week)
escalation	Cohort 5	3-6	2.5 mg (daily, Cycle 1 Day 1-5)	1.5 mg (three times per week)
	Cohort 6	3-6	3 mg (daily, Cycle 1 Day 1-5)	2 mg (three times per week)
Expansion	Cohort 7	12	RP2D	RP2D

\*Intermediate induction or maintenance doses of IACS-010759 may be pursued with SMC approval, not to exceed 6 mg, and

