# alternative duration of induction doses or other maintenance schedules not listed above may also be pursued with SMC approval depending on the safety, PK and PD data observed.

\*\*Following their review of Cohort 3, the SMC recommended implementation of the following dose schedule for

subjects who enroll in Cohort 4 of the study:

Induction dose: 2.5 mg, administered daily, Cycle 1 Day 1 through Day 7

Maintenance dose: 1 mg, administered 3x/week (for a total weekly dose of 3 mg) with the first maintenance dose starting on Cycle 1 Day 8

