### 6 Study Drug

### 6.1 Study Drug Administration

Cohorts 1 and 2: For each cycle 1, a single oral dose of IACS-010759 will be administered on day 1. The next dose of IAC-010759 will be administered on day 8, and daily continuously for the duration of the study with no interruptions unless there are adverse events as described in Section 4.1.9. IACS-010759 doses will be separated by intervals of approximately 24 hours (+/- 3 hours).

Cohorts 3-6 and Dose Expansion: Based on the observed accumulation of IACS-010759 throughout the dosing period in cohorts 1 and 2, a modified dosing regimen is being implemented, consisting of an induction phase in which IACS-010759 is administered daily for up to 7 days, followed by a maintenance phase in which a lower dose is administered weekly (or as otherwise specified by the SMC based on safety, PK and PD data observed) to maintain steady state plasma levels. Dosing will proceed on this schedule for the duration of the study with no interruptions unless there are adverse events as described in Section 4.1.9.

IACS-010759 will be administered without food, at least 1 hour before and at least 2 hours after eating. Each dose of IACS-010759 should be administered with 8 ounces of water. If a dose is missed, the next dose will not be increased to account for missing a dose. The subject will take the next regular dose at the scheduled time. Following cycle 1 (28-day cycle for cohorts 1 and 2, 21 day cycle for subsequent cohorts), subjects will receive one cycle of therapy every 21 days (+/- 4 days).

In cohorts 1 and 2, treatment was administered as an inpatient for 24 hours on day 1 and then starting on day 8 for the next 7 days for all enrolled subjects. In cohorts 3 and 4, treatment will be administered as an inpatient for 24 hours on Day 7 of Cycle 1 for all enrolled subjects. In subsequent cohorts, treatment will be administered as an inpatient for 24 hours on Day 5 of Cycle 1 for all enrolled subjects. IACS-010759 will be self-administered and subjects instructed not to dose on days when PK/PD samples are collected until advised by the research staff. Self-administration can occur on days without PK/PD and subjects will record administration in a provided diary.

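### Minor, and only if the RP2D has more than 5 induction days: cohort 7's end-of-induction ECG, PD draw, serial PK and vital signs, and inpatient stay remain fixed on Cycle 1 Day 5, before the last induction dose.

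*Combined protocol and SAP*

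**What the plan says.** Section 4.1.8 treats expansion subjects at the RP2D. Table 2 (section 4.1.6) gives cohort 7 as 12 subjects with RP2D entered for both induction and maintenance, so its induction length is not fixed in advance.

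Cohort 7 has no flowchart of its own. Section 4.2 combines it with the two 5-day cohorts under the title "Cohorts 5-6 Dose-Escalation and Cohort 7 Dose-Expansion". That chart has a Cycle 1 Day 5 column with no day window and has no Day 7 column. On Day 5 it schedules:

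- ECG and PD draw, pre-dose and at 4 h;
- vital signs to 8 h;
- serial PK to 8 h, plus a sample at "24 hours (+/- 2 hours) post study drug administration";
- the inpatient day: "Treatment will be administered as an inpatient for 24 hours on Day 5 of Cycle 1".

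Section 6.1 repeats the inpatient day without condition: "In subsequent cohorts, treatment will be administered as an inpatient for 24 hours on Day 5 of Cycle 1 for all enrolled subjects". Footnote P refers to Table 2 for dosing, not for visit days: "The dose regimen for the induction and maintenance doses are provided in Table 2".

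The 7-day cohorts are handled differently. Cohort 4 induction is "2.5 mg (daily, Cycle 1 Day 1-7", and cohort 3 also runs Days 1-7. Their flowchart places the same assessments on Day 7, with the inpatient stay there too: "Treatment will be administered as an inpatient for 24 hours on Day 7 of Cycle 1".

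**The concern.** Amendment 10 moved this visit from Day 7 to Day 5 when induction was shortened from cohort 5 onward, so the visit appears meant to follow the last induction dose. For cohort 7 the regimen is left open and the visit day is not. If the RP2D has a 7-day induction, the ECG, PD draw, serial profile and inpatient observation come two doses early.

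What is at stake is observation at the end of loading. Section 4.1.11 names lactic acidosis as a potential mechanism-based effect, and section 3.1 reports unexpected accumulation in cohorts 1 and 2. The last induction dose is therefore a sensible time for the ECG and the inpatient day, and the 12 new subjects would not have them scheduled then.

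**Working it through.** **1. Can the RP2D have more than 5 induction days?** Yes, by three routes.

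- Section 4.1.7: 2 or more DLTs in cohort 5 make the prior cohort's level, cohort 4 (Days 1-7), the MTD level.
- Section 4.1.7: a lower dose level may be expanded without an MTD having been reached.
- Table 2 footnote: "alternative duration of induction doses or other maintenance schedules not listed above may also be pursued with SMC approval".

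For the first route, with a true cohort 5 DLT rate p (assumed), the standard 3+3 chance of stepping back is P(2 or more of 3) + P(exactly 1 of 3) × P(1 or more of the next 3). At p = 0.20 this is 0.104 + 0.384 × 0.488 = 0.29. At p = 0.10 it is 0.09 and at p = 0.30 it is 0.51. These are chances of stepping back given p, not chances of a 7-day RP2D.

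**2. Where does Day 5 fall?** Dosing is daily from Day 1, so Day 5 is dose 5. For cohort 4 that is 5 × 2.5 = 12.5 mg of 7 × 2.5 = 17.5 mg. For cohort 3 it is 10 mg of 14 mg. Both are 71%.

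**3. What remains scheduled after Day 5 in the cohort 7 chart?** PK, lactate/pH and vital signs, pre-dose and at 4 h, on Day 8. ECG and PD on Days 15 and 21. There is no ECG or PD draw on Day 7 or Day 8.

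**4. How far below the Day 7 peak would the assessments be?** The documents give no human half-life; the animal range in section 2.2.2 is 42-57 h. I assumed one compartment with instantaneous absorption and half-life h, so r = 2^(-24/h) and each day's level = previous level × r + dose. Maintenance was taken as 1 mg on Days 8, 10, 12, 15, 17 and 19 for cohort 4 (days assumed) and 0.5 mg on Days 8 and 15 for cohort 3 (synopsis). The Day 5 ratio to the Day 7 peak is (1 - r^5)/(1 - r^7) for either regimen.

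Cohort 4 regimen, % of the Day 7 post-dose level:

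| Half-life | Day 5 | Day 8 post-dose | Day 15 post-dose | Day 21 | Best ECG/PD day |
|---|---|---|---|---|---|
| 42 h | 92 | 81 | 25 | 12 | 92 |
| 57 h | 88 | 86 | 30 | 15 | 88 |
| 200 h | 77 | 99 | 73 | 56 | 77 |
| 500 h | 74 | 103 | 99 | 93 | 99 |
| No elimination | 71 | 106 | 123 | 134 | 134 |

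As the half-life grows, the Day 5 ratio falls and the Day 15 ratio rises, so the worst case for the best-placed ECG/PD day lies where they cross. Searching 30-3000 h:

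- Cohort 4: 221 h. r^5 = 0.686 and r^7 = 0.590, giving 0.314/0.410 = 76.6%.
- Cohort 3: 342 h. r^5 = 0.784 and r^7 = 0.711, giving 0.216/0.289 = 74.8%. Its weekly 0.5 mg maintenance lets Day 15 catch up only at a longer half-life.

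Section 3.1 describes clearance falling exponentially. With k(t) = k0·exp(-t/tau), an assumed starting half-life of 42-57 h and tau of 2-60 days, the worst cases are 78.7% (cohort 4) and 75.5% (cohort 3).

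**The case against.** The strongest reply is that nothing is wrong with the plan as it stands. Cohorts 5 and 6, the only planned escalation regimens on this flowchart, have 5-day induction, so Day 5 is right for them. The SMC recommended shortening from 7 to 5 days, which makes a 5-day RP2D the natural expectation. Visit days were also revised when induction changed in Amendments 5 and 10, so a provisional schedule for a dose not yet chosen is normal. This stands as to likelihood and weight. It does not remove the point: the amendment log says the SMC was given authority over induction duration so that no protocol amendment would be needed, and so nothing guarantees that the flowchart would be revisited.

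Footnotes K and M also count. They allow extra PK, lactate and pH draws at the investigator's discretion, so a Day 7 PK profile is permitted though not scheduled. They do not cover the ECG, PD draw or inpatient stay.

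Two stronger readings are tempting.

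- A reader might infer that a stop at cohort 5 forces a 7-day RP2D. It does not. Cohorts 4 and 5 share the 2.5 mg induction dose, and the SMC may choose another duration.
- A reader might infer that primary safety decisions are compromised. They are not. The expansion rule in section 4.1.8 counts first-cycle DLTs whatever the visit day. The Day 7 and Day 8 concentration rules in section 4.1.7 govern escalation only. The food effect is assessed on Day 1.

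**Conclusion.** The point holds as a minor one, conditional on an RP2D with more than 5 induction days. In that case the 12 new subjects have no scheduled ECG, PD draw, serial PK or vital signs, or inpatient observation at the last induction dose. With a 5-day RP2D there is no mismatch.

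The consequence is small. The best-placed scheduled ECG and PD draw would be at about three-quarters of the Day 7 peak at worst, and for the cohort 4 regimen the Day 8 samples would be at 81-106% of it. If cohort 4 is the RP2D, that cohort is filled to 6 subjects before expansion, and its own schedule has these assessments on Day 7. Nonclinical QT concern is low (section 2.2.2) and PD is an exploratory objective. All the percentages rest on assumed kinetics and should be read as a rough size only. That a longer induction is reachable, and that Day 5 is fixed, rest on the text alone.

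**What to change.** For cohort 7, replace Day 5 with *last induction day of the RP2D regimen* in the flowchart's Study Day and Cycle Day labels, in its inpatient footnote and in section 6.1. Keep the present absence of a day window. Do not list particular days: naming only Day 5 and Day 7 would recreate the mismatch for another SMC-approved length, such as 6 days. If induction lasts 7 days, state that the Day 8 pre-dose PK sample, taken 24 h (+/- 2 h) after the Day 7 dose, serves as the 24 h sample.

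A simple reference to the cohort 3-4 flowchart would not do. Its dosing row shows maintenance only on Days 8 and 15, whereas cohort 4 doses three times per week, and its Day 7 and Day 8 columns allow +/- 1 day, while Amendment 10 removed the Day 5 and Day 8 windows for PK consistency.

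The cost is a few labels, one footnote and one sentence. No visits, samples or ECGs are added, and nothing changes under a 5-day RP2D. The only downside is the tighter Day 8 limit for a 7-day regimen, because pre-dose now means any time on the dosing day.
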